6. RISK/BENEFIT

POTENTIAL RISKS. The major risk of research participation is related to drug administration. It is worth noting that we have had vast experience thus far administering a range of abused drugs, including cannabis, cocaine, amphetamines, opioids, and ethanol, and have used oral, intravenous, intranasal, and smoked, routes of administration. We also have experience with the amount of cannabis proposed in the current study with no adverse consequences. Many of the assessments for this study involve minimal physical, psychological, social, or other risks risk to the participants such as answering questionnaires, physical examination of gait, and performance of simple tasks such as balancing with feet in a tandem position. The timed gait assessments do not require attachment to any monitoring devices. Thus the risks are expected to be similar to those risks involved in everyday standing, stair climbing, walking, and activities of daily living. Subjects might tire during the mobility test. Research assistants will closely monitor subjects for tiredness, loss of balance, or any other physical discomfort symptoms, and stop testing or institute rest breaks as needed.

Participation in research may involve a loss of privacy; however every effort is made to insure the confidentiality of the participant. All samples and study information will be coded onto forms that will be kept in locked files at all times. Confidential information is maintained in a locked cabinet that is accessible only to study personnel. Staff has been trained in the procedures necessary to insure confidentiality. No individual identities will be used in any reports or publications resulting from the study.

Possible side effects of smoked cannabis include: sedation, gait disturbance, tiredness, sadness, anxiety, concentration difficulties, increased heart rate, palpitations, dizziness, sleep disturbance, changes in food intake, restlessness, confusion, sleepiness, clumsiness, gastrointestinal upset, headache, nausea, dry mouth, pallor, flushing, sweating, and slurred speech. All participants will be carefully monitored and fully informed of the side effects that they might experience. Because all currently smoke cannabis, these effects should be familiar to them. Inactive and active cannabis cigarettes are provided by NIDA to [name] Research Laboratory, which has conducted federally funded, placebo controlled human laboratory studies of cannabis administration for the past 20 years, including studies that include HIV-infected volunteers. [name] has FDA, DEA and NY State Narcotics licenses to conduct federally funded studies testing the behavioral effects of cannabis. Participants will be closely monitored by staff during the balance and walking task to prevent actual falls.

ADEQUACY OF PROTECTION AGAINST RISKS. All participants are fully informed of the side effects that they might experience. Only those judged suitable are invited to participate in the full study. Throughout participation, we will carefully monitor participants for agitation, hostility, depression, or changes in behavior, thinking, or suicidal thoughts or actions, anxiety, panic, aggression, anger, mania, abnormal sensations, hallucinations, paranoia, or confusion.

Emergency medical equipment is available in [name] laboratory, which is located adjacent to New York Presbyterian Hospital so a full medical emergency back-up team is available. We anticipate, however, that careful screening, informed consent, cannabis dose selection, and participant monitoring, will obviate the need for such emergency care. [name] has been conducting inpatient and outpatient clinical pharmacology research for over 20 years.

Confidentiality issues: Participation in research may involve a loss of privacy. We deal with issues of confidentiality by using coded records, store signed consent forms in a locked safe, and trying to the best of our ability to maintain confidentiality. All participants are assigned a study number that is used as identification on all data sheets and laboratory requests. The participants' names are listed on a separate log that is kept with locator information in a locked file in a locked room separate from the data file room. No individual identities will be used in any reports or publications resulting from the study. All key personnel, including anyone who interacts with the participants in the collection of data, have completed training courses on the Protection of Human Research Subjects. The Department of Health and Human Services has issued a Certificate of Confidentiality to MWCCS ensuring that all confidential and personal information provided remains confidential, and cannot be requested or utilized by other official

governmental or local agencies.

NIH Requirements for Education in the Protection of Human Research Participants: All key personnel on this grant have passed the Einstein or Columbia University "Good Clinical Practices" examination, and received certificates indicating they had learned the necessary information covered by that course. The information covered in this comprehensive one-day course includes knowledge of the regulations guiding clinical research as well as ethical issues involved in research with human participants. In addition to this formal examination, all key personnel on this project will participate in two one-hour sessions discussing ethical issues involved in research with human participants that included the Belmont report, the NIAAA and NIDA guidelines for administration of alcohol and drugs of abuse to humans, and a discussion of the regulations promulgated by HHS for carrying out research with human participants.

POTENTIAL BENEFITS OF PROPOSED RESEARCH. There are few direct benefits to research volunteers in the proposed study. Results from this study may eventually benefit women who use cannabis by providing important information about balance, mobility, and cognitive disorders associated with cannabis use and HIV infection. Prior to study acceptance, all volunteers will be screened for medical and psychiatric exclusion criteria. Volunteers understand that they can obtain a referral for drug treatment at any stage of their research participation. We repeat our offer for treatment referral at screening, and at discharge from the study. We will attempt to obtain a placement in a drug abuse clinic for those people who indicate a desire for help, and will inform all volunteers of our ongoing cannabis-treatment studies conducted within the Division of Substance Abuse.

IMPORTANCE OF THE KNOWLEDGE TO BE GAINED. The risk/benefit ratio for these studies appears favorable. The major benefit of this research is scientific. Despite its therapeutic benefits, cannabis use may also be associated with adverse health outcomes, particularly among aging HIV+ populations. An improved understanding of the effects of cannabis use on balance, mobility, and cognition and their relation to fall risk may have important implications for developing effective risk assessments and intervention procedures to reduce the burden of mobility impairments in aging women who use cannabis, with or without HIV. We anticipate that the degree of risk to which individuals are exposed will be small due to the care with which these studies will be carried out. The potential benefits to society in terms of the knowledge gained are substantial because it will lead to a better understanding of the acute effects of cannabis use on gait, balance, and cognition, in aging women with our with HIV infection. Consequently, we believe the conduct of this research is well justified.

7. DATA ANALYSIS

OVERVIEW AND APPROACH: To determine the acute effects of cannabis on balance, mobility, and cognition among older HIV+ and HIV- women.

OUTCOMES: Primary outcomes are functional reach and gait speed (Aim 1) and number of correct suppressions on the Sustained Attention to Response Task (SART) (Aim 2) under active and inactive cannabis

STATISTICAL ANALYSIS: Descriptive data analysis will identify erroneous values, outliers, distributional properties, and insufficient data dispersion for making analytic comparisons. As needed, transformations such as logarithmic or categorization will be applied to skewed continuous variables. The HIV+ and HIV-arms will be compared using t-tests/ANOVA, and/or rank tests for continuous and exact tests for binary baseline covariates to identify potential confounders and generalizability issues. Within our crossover design for the outcomes of both Aims 1 and 2 with each subject getting both active and inactive cannabis (after verifying distributions are not too skewed for normal approximation), we will use linear mixed effects models, which take account of correlations among measurements within the same subjects, to compare functional reach and gait speed (Aim 1) and number of correct suppressions on the Sustained Attention to Response Task (SART) (Aim 2) after inactive vs. active cannabis administration, and to evaluate whether HIV+ women have greater declines in gait speed and functional reach and attention than HIV- women, after administration of active vs. inactive cannabis (i.e. by fitting interaction terms). In these models the 15, 60, 105 and 150 minute measures with baseline from the same visit subtracted will be the outcome(s). Because peak marijuana effect is expected to occur on 15 to 60 minutes, for the

purpose of effect size estimation, averaged 15 and 60 minute results (with baseline subtracted) will be the primary outcome(s) and this analysis reduces to a two way ANOVA or equivalently two sample t-test of differences in differences. Other quantitative and descriptive approaches previously applied to these measures¹⁰⁴ including area under the curve and trajectories will be fit.

POWER CALCULATIONS: Under the standard approach to power estimation of hypothesis testing at a two sided α =0.05 with β =0.2, this study even with only 60 subjects is powered to detect (active vs. inactive cannabis) effect sizes of at least 0.53 for functional reach and 0.63 for walking time, both of which are considered to be medium. The power here is greatly increased by repeated measures being taken pre and post administration with the outcome being the difference of averaged measures that from our normative data have correlations of ρ =0.82 an 0.87 for walking time and functional reach which reduces the variances of within subject difference to 0.27 σ 2 and 0.195 σ 2 respectively. We do not have similar normative data for power estimation of other outcomes. Some authors believe that in pilot studies that will be later confirmed 105-107 a higher α =0.25 is appropriate, in which case, the detectable effect sizes drop to 0.32 for reach and 0.38 for walking time which are considered close to small. Other criteria besides hypotheses testing that are satisfied by smaller sample sizes should be considered for pilot studies 107-109 with other authors finding 20-70 subjects adequate for estimating standard deviations 110-112 and effect sizes 112,113 of outcomes and identification of subject exclusion criteria for the main study.

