2. STUDY DESIGN

Specific Aims and Hypotheses

Aim 1. To compare the acute effects of cannabis on balance and mobility among older HIV+ and HIV- women. We will quantify the effects of active and inactive cannabis in HIV+ and HIV- participants. We hypothesize that, following active cannabis administration, HIV+ women will perform worse than HIV- women on tasks measuring balance and mobility, especially under walking conditions that demand attention. HIV+ and HIV- women will not differ in performance under inactive cannabis conditions.

Aim 2. To compare the acute effects of cannabis on cognition among older HIV+ and HIV- women. We will assess effects of active and inactive cannabis on the Sustained Attention to Response Task (SART) in HIV+ and HIV- women. We hypothesize that following active cannabis administration, HIV+ women will perform worse than HIV- women on cognitive testing of attention. The groups will not differ following inactive cannabis administration.

OVERVIEW OF STUDY APPROACH

The WIHS is the largest and longest running cohort of HIV+ women and their matched HIV- controls in the U.S. and has now merged with the Multicenter AIDS Cohort (MACS) to form the MWCCS. We propose to explore potential mechanisms that underlie the increased fall risk associated with cannabis use observed in aging women with HIV infection in the former WIHS/current MWCCS relative to those without HIV. We will compare between-(HIV+ and HIV-) and within- (active vs placebo cannabis) subject effects of cannabis on measures of balance, mobility, and cognition, including a cognitive-motor divided attention task (WWT), under supervised administration of active (7.0% THC) and inactive (0.0% THC) cannabis in older HIV+ women on stable HAART and HIV- controls enrolled in the MWCCS.

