- c. Balance Testing: (1) One Leg Stand (OLS): participant stands on one foot with the other stretched out ~6" off the floor for 30 seconds while counting aloud by thousands, and is observed for body sway, use of arms to maintain balance, hopping, or putting raised foot down. 96 (2) Walk and Turn (WAT): participant takes nine heel-to-toe steps along a straight line, counting steps aloud, turns on the planted foot, and returns in the same manner. The participant is observed for losing balance while listening to instructions, starting too soon, stopping while walking, missing heel-to-toe, stepping off the line, using arms to balance, incorrect number of steps, and improper turn. Standardized Field Sobriety Tests (SFST) include the OLS and WAT, along with Horizontal Gaze Nystagmus (HGN). 96-98 (3) Modified Romberg Balance Test (MRB) detects the ability to maintain a steady standing posture with eyes closed, as well as divided attention and time sense impairment.99 The participant stands with her feet together, head tilted backward, and eyes closed, estimates the passage of 30 seconds, and is observed for body sway and direction, accuracy of 30 second time, and eyelid and body tremors. These balance tests challenge the ability to divide attention between remembering directions while simultaneously performing a physical task, and are thus considered divided attention tests. 100 (4) Functional Reach: this test of dynamic balance measures the distance the subject can reach in front of her from a standing position without losing balance. 101,102
- **d.** Cognitive Task Battery: A 25-minute battery assessing cannabis effects on attention, processing speed, recognition memory, and Reaction Time/Response Inhibition ¹⁰³ will be completed 4 times per session.

(1) Sustained Attention to Response Task (SART)

Length of time: 6 minutes

Measures: Attention

Task: Participants are presented with a single digit 1-9 in the middle of the screen in varying font sizes. The digit disappears after a short while and is replaced with a mask (circle with an X). Participants are asked to press the SPACEBAR if any digit other than 3 is presented and to withhold the response if digit 3 presented.

Main outcomes: (1) number of correct suppressions; (2) number of incorrect suppressions; (3) mean reaction time

(2) Digit Symbol Substitution Task (DSST)

Length of time: 3 minutes **Measures**: Processing Speed

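### The Aim 2 primary, SART correct suppressions alone, credits non-response as good attention, so cannabis-induced omissions would bias the active-versus-inactive contrast toward no effect or apparent improvement

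*Combined protocol and SAP*

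**What the plan says.** Section 2 (Cognitive Task Battery, SART) instructs participants to "press the SPACEBAR if any digit other than 3 is presented and to withhold the response if digit 3 presented". It then lists three results: "Main outcomes: (1) number of correct suppressions; (2) number of incorrect suppressions; (3) mean reaction time".

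Section 7 carries only the first of these forward. The Aim 2 primary is the "number of correct suppressions on the Sustained Attention to Response Task (SART) (Aim 2) under active and inactive cannabis", and the same count is the outcome of the mixed model. The primary summary is the mean of the 15- and 60-minute readings minus the same-visit baseline. It is compared between active and inactive cannabis and, through the interaction, between HIV groups. The Aim 2 hypothesis in section 2 is directional: after active cannabis, "HIV+ women will perform worse than HIV- women on cognitive testing of attention".

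Section 7 mentions neither incorrect suppressions nor reaction time. It has a general check for outliers and distributions, but no rule for a run with little responding. Section 6 gives the drug's possible effects: "Possible side effects of smoked cannabis include: sedation, gait disturbance, tiredness, sadness, anxiety, concentration difficulties", with sleepiness later in the same list.

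**The concern.** A correct suppression is the absence of a key press on a 3. The count cannot tell a woman who saw the 3 and held back from one who was not responding at all. A woman who never presses scores the maximum.

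The primary window was chosen because peak drug effect is expected there, so any non-response caused by the drug would fall inside it. Same-visit baseline subtraction and the inactive session do not remove omissions that arise only after active dosing.

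The pilot is meant to yield effect sizes and feed a further grant application. A diluted or wrong-signed estimate of the cannabis effect on attention would carry into the next study.

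**Working it through.** **Plan's own figure.** There is none to reproduce. The power paragraph in section 7 covers functional reach and walking time and says that similar normative data are lacking for other outcomes. The protocol gives no SART trial count, share of 3s, response deadline, SD or expected value.

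**Model.** Let *s* be the probability of withholding on a 3 when engaged, and *l* the probability of giving no response on any trial. I read an incorrect suppression as no press on a digit other than 3; the protocol does not spell this out. All values of *s* and *l* below are assumptions.

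- Correct-suppression rate = l + (1 − l)s. Its slope in l is 1 − s, which is never negative. At l = 1 it equals 1 for every s.
- Incorrect-suppression rate = l.
- Difference = (1 − l)s, which falls if s falls or l rises.

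**Active versus inactive, worked cases**

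| s | l | Correct-suppression rate | Difference score |
|---|---|---|---|
| 0.50 | 0 | 0.50 | 0.50 |
| 0.50 | 0.20 | 0.20 + 0.80 × 0.50 = 0.60 | 0.40 |
| 0.40 | 0.17 | 0.17 + 0.83 × 0.40 = 0.502 | 0.332 |
| 0.70 | 0 | 0.70 | 0.70 |
| 0.60 | 0.25 | 0.25 + 0.75 × 0.60 = 0.70 | 0.45 |

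The rates do not depend on the number of trials. If there were 25 digit-3 trials and 200 others (assumed), the second row would be 15.0 correct suppressions instead of 12.5, with about 40 incorrect suppressions instead of 0.

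**Non-response that fully hides a fall from s0 to s1** (no omissions at comparison): l* = (s0 − s1)/(1 − s1).

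- Fall of 0.05: 0.05/0.55 = 9% at s0 = 0.50, up to 0.05/0.25 = 20% at s0 = 0.80.
- Fall of 0.10: 0.10/0.60 = 17% at s0 = 0.50, up to 0.10/0.30 = 33% at s0 = 0.80.

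Above these rates the sign reverses; below them the effect is diluted.

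**HIV contrast, equal omissions.** With equal starting values and the same post-dose l in both groups, the planned contrast is (1 − l)(s_HIV+ − s_HIV−). At l = 0.20, a true −0.10 becomes −0.08. The difference score subtracts the same l from both groups and gives the identical contrast.

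**HIV contrast, unequal omissions.** Assume s = 0.60 and l = 0.02 at baseline and after inactive cannabis, and s = 0.45 (HIV+) and 0.55 (HIV−) after active. The planned 30 versus 30 t-test of differences in differences was simulated with 2,000 runs, 25 and 200 trials, and between-woman SD 0.6 on the logit of s.

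| Active l, HIV+ / HIV− | Planned contrast, formula | Planned contrast, simulated | Significant at 0.05 | Difference score, simulated |
|---|---|---|---|---|
| 2% / 2% | −0.098 | −0.090 | 56% | −0.090 |
| 10% / 5% | −0.0675 | −0.060 | 29% | −0.110 |
| 20% / 5% | −0.0125 | −0.006 | 5% | −0.155 |
| 25% / 5% | +0.015 | +0.021 | 7% | −0.179 |
| 35% / 5% | +0.070 | +0.077 | 43% | −0.223 |

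The formula column is [l + (1 − l) × 0.45] for HIV+ minus [l + (1 − l) × 0.55] for HIV−. Formula and simulation differ slightly because s varies between women.

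**The case against.** The strongest objection concerns the HIV hypothesis. A reader might infer that if cannabis makes women miss responses, Aim 2 will miss or reverse the HIV difference. The documents do not support that. With equal omissions the HIV contrast only shrinks, keeps its sign, and is the same under either score. Hiding it took about 20% versus 5% in the assumed example, and no section suggests that omissions differ by HIV status. This stands and limits the point.

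A reader might also infer that any lapse, or any slowing, inflates the score. Lapses into automatic pressing lower it, as intended. Slowing cannot be assessed because no response deadline is given. Both limits stand.

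Nor do the documents predict the omission rates used. Section 6 lists only possible effects, the acute cognitive effects in section 1 are described in young people, and SART omissions are not mentioned anywhere. This stands: the direction of the bias is derived, its size is not.

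It can also be said that incorrect suppressions and reaction time are recorded anyway, that this is a pilot, and that a difference score merges failed inhibition with omission. The recording helps only in part, because section 7 does not commit to analysing or reporting those measures. Pilot status does not make an ambiguous effect size more useful. The merging is a real drawback, met by reporting the components.

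**Conclusion.** The point holds in a limited form. By the protocol's own task rule, the Aim 2 primary rises with non-response, and nothing in section 7 corrects for it. The active-versus-inactive contrast is therefore open to bias toward no effect or apparent improvement if active cannabis increases omissions. Under the assumed values, full masking of a 0.10 loss in withholding needs 17% to 33% non-response, and lower rates dilute it. The HIV contrast is at risk of being hidden or reversed only if omissions are sufficiently higher in HIV+ women.

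The scoring logic is certain. How often the bias would occur is unknown, because it depends on omission rates that the documents do not give. This is a worthwhile, inexpensive improvement; it does not show that the planned result will be wrong.

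**What to change.** In section 7, before unblinding, define the Aim 2 attention score as the correct-suppression rate on digit-3 trials minus the incorrect-suppression rate on all other trials; d-prime is an alternative. Define an incorrect suppression explicitly and state the trial numbers. Keep the same-visit baseline subtraction and the 15/60-minute average. Report correct suppressions, incorrect suppressions and mean reaction time as components.

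If the sponsor keeps the count as primary, pre-specify the discrimination score as a supporting analysis for both the active-versus-inactive and the HIV contrasts. State also that a null or improved count will not be read as preserved attention when incorrect suppressions rise.

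The cost is a short change to section 7 and one variable derived from data already recorded. No stated power is lost, because none is given for SART. The score is less familiar, and a change in it cannot be attributed to inhibition or to omission without the components.

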STUDY SETTING The WIHS, established in 1994, was a prospective cohort study of HIV disease progression in women from 9 US cities, in which HIV+ and HIV- participants are well-matched by age, race/ethnicity, education, and high-risk sexual and substance use behavior. 86,87 Semi-annual visits included in-depth interviews, physical exam, and collection of blood, oral, gynecologic, and urine specimens. Current visit structure is now annual in MWCCS. Interviews include sociodemographics, medical history (HIV- and non-HIV related), medication use, HAART use and adherence, substance use, and report of falls and fall-related injury, among others. A neurocognitive testing battery is performed every two years. 88,89 MWCCS has a central Data Analysis and Coordination Center (DACC) and an extensive repository of biological specimens. The Cannabis Research Laboratory, Columbia University Medical Center (CUMC), is directed by [name]. Her laboratory has been conducting federally-funded, placebo-controlled human laboratory studies of cannabis administration for the past 20 years, including studies with HIV+ research volunteers. By collaborating with [name], we have the opportunity to directly assess the acute effects of active vs inactive cannabis administration on a range of clinically-relevant outcome measures, thereby dissociating expectancy effects of cannabis from its pharmacological effects.

STUDY PARTICIPANTS.

We will recruit and test 60 women who report cannabis use within the past six months, including 30 HIV+ women and 30 demographically similar HIV- controls from the Bronx and Brooklyn MWCCS sites, and from clinical populations, such as patients receiving care at Einstein/Montefiore Medical Center, other medical facilities, referred by medical providers, or word-of-mouth if eligibility can be confirmed. Median age of Bronx MWCCS participants is 54 years, with 75% between 49 and 59 years. Inclusion Criteria: (1) current cannabis use (within 6 months) based on self-report, (2) able to perform study procedures, including ability to ambulate independently, (3) adequate hearing and vision, (4) for HIV+ women, use of stable HAART for at least 6 months. Participants must be willing to smoke cannabis during both study

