Study Design (Table 1): A within-subject design will be used in which all participants will experience active and inactive cannabis, thereby increasing statistical power. Participants will be instructed to refrain from using any drugs for or tobacco cigarettes beginning at midnight prior to each session and to abstain from drinking alcohol for at least a 24-hour period prior to testing. A urine drug screen, breathalyzer, carbon monoxide (CO), and pregnancy test will be conducted upon arrival at the laboratory to confirm compliance. If there is evidence of illicit drug, alcohol, or cannabis use on the morning of the session based on CO, the session will be rescheduled. At the beginning of each session, a timeline follow-back questionnaire querying cannabis, alcohol, and other drug use will be completed. Participants will be offered a light breakfast (bagel or cereal, juice, coffee). Following breakfast, baseline cardiovascular measures (heart rate and blood pressure measurement), subjective effects questionnaires, and performance tasks will be completed. Tobacco cigarette smokers will be given up to two smoking breaks per session scheduled at the same time for both sessions in order to minimize nicotine withdrawal symptoms. The participant and study staff will be blind to cannabis cigarette content. Cardiovascular and subjective effects measures, mobility and balance testing, and a cognitive task battery will be completed at baseline and at 15–120 min intervals following cannabis administration. At the end of each session, participants will be carefully assessed to ensure they are no longer intoxicated, and may leave after passing field sobriety and balancing tasks. Participants unable to pass field sobriety testing will remain in the Research Laboratory until they are no longer intoxicated, pass repeat field sobriety testing, and can safely be discharged. They will be compensated for this additional time.

| Table 1 | Table 1. Time Course of Sessions | | | | | | | | | |
|---------|--|-----|--|--|--|--|--|--|--|--|
| Time | Event | | Event | | | | | | | |
| -60 | Begin session: urine toxicology, CO, breathalyzer, pregnancy testing timeline flow-back questionnaire, breakfast | 105 | Vitals, subjective effects, MRF, mobility, balance and cognitive batteries | | | | | | | |
| -30 | Field sobriety, vitals, subjective effects, mobility, balance and cognitive batteries | | | | | | | | | |

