| 0 | Cannabis administration | 150 | Vitals, subjective effects, MRF, mobility, balance and cognitive batteries | | | | | | | |
| 15 | Vitals, MRF (Marijuana Rating Form), subjective effects, mobility, balance and cognitive batteries | 180 | Lunch/snacks | | | | | | | |

| 60 | Vitals, MRF, subjective effects, mobility, balance and cognitive batteries | 210 | Field sobriety, end session | |
|----|--|-----|-----------------------------|--|
|----|--|-----|-----------------------------|--|

- **a.** Behavioral Measurements: (1) Subjective Effects Ratings: A 3-minute series of visual analog scales (VAS) in which participants indicate how they are feeling at that moment will be done 4 times over the course of the study visit. This 44-item scale assesses the effects of cannabis on a range of affective and physical symptoms (e.g., friendly, mellow, sedated, anxious).⁹⁰ (2) Marijuana Rating Form: Cannabis-related effects are assessed using a five-item visual analog scale asking participants to rate the strength of the cannabis effect, good effect, bad effect, drug liking, and willingness to smoke the cannabis again. Participants also indicate whether they think cannabis is active or inactive.
- **b.** Mobility testing: Timed gait and Walking While Talking (WWT). Gait speed is measured under normal walking and attention-demanding conditions. There are two single task conditions: 1) Normal Walk (NW): participants are asked to walk 20 ft at their "normal pace" and are timed; and 2) Cognitive (Alpha): participants stand still while reciting alternate letters of the alphabet starting with the letter B for 30-sec out loud. In WWT, participants walk 20 ft at their normal pace while reciting alternate letters of the alphabet starting with the letter 'B' and are instructed to pay equal attention to both tasks.^{28,91} The three test conditions are presented in a counterbalanced order using a Latin-square design. Reliability and validity for this walking paradigm have been established.^{30,92} The main comparison is between NW and WWT; cognitive performance is also quantified with the number of correct letters and errors generated.⁹³⁻⁹⁵

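### Subtracting each session's baseline is valid, but in this crossover it is generally somewhat less precise than adjusting for that baseline; the documents do not fix the size of the loss

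*Combined protocol and SAP*

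**What the plan says.** Section 7, Statistical analysis, uses linear mixed models for all three primary outcomes and defines the response as follows: "In these models the 15, 60, 105 and 150 minute measures with baseline from the same visit subtracted will be the outcome(s"). For effect size estimation it then narrows to the expected peak: "averaged 15 and 60 minute results (with baseline subtracted) will be the primary outcome(s"). This reduces to a two-sample t-test of differences in differences between HIV+ and HIV- women. The session baseline is not entered as a covariate anywhere.

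The outcomes paragraph states: "Primary outcomes are functional reach and gait speed (Aim 1"), with SART correct suppressions for Aim 2. The power paragraph gives correlations of 0.82 "an 0.87 for walking time and functional reach which reduces the variances of within subject difference to" 0.27σ² and 0.195σ². It adds: "We do not have similar normative data for power estimation of other outcomes".

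In section 2, every woman smokes both strengths in counterbalanced order, at visits at least 48 hours apart. Table 1 places a full mobility, balance and cognitive battery at -30 minutes in each session, so the covariate needed for adjustment is already collected.

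**The concern.** In a parallel-group trial, subtracting baseline removes stable differences between people. In a crossover, the active-minus-inactive contrast of post-dose values has already done that. What the session baselines add is information on how a woman's state that day differed between her two visits. Subtraction carries that day-to-day difference, and the measurement error in both baselines, forward at full weight. Regression gives it the weight the data support.

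What is at stake is interval width. The sample is fixed at 60, and the 15/60-minute outcome is set for effect size estimation in a pilot. If the weight of 1 is too large, the intervals are wider than the collected data require.

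**Working it through.** **Inputs from the plan.** Correlations ρw = 0.82 (walking time) and 0.87 (reach); 30 HIV+ and 30 HIV- women; one baseline and the mean of two post-dose values per session.

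**Inputs assumed.** The between-visit correlation ρb; the variance h of the individual active-minus-inactive response, independent of baseline; equal SDs; and ρw read as a within-visit correlation.

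**Reproducing the plan's figure.** With equal within-visit correlation, the mean of two post-dose values minus baseline has variance σ²[(1+ρw)/2 + 1 - 2ρw] = 1.5(1-ρw)σ².
- Walking time: 1.5 × 0.18 = 0.27.
- Reach: 1.5 × 0.13 = 0.195.

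Both match the power paragraph.

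**Two estimators.** Let P be the active-minus-inactive difference in post-dose means and B the same difference in baselines. In units of σ²:
- Var(P) = 1 + ρw - 2ρb + h
- Cov(P,B) = 2(ρw - ρb)
- Var(B) = 2(1 - ρb)
- Subtraction: Var(P - B) = 3(1 - ρw) + h
- Best coefficient: Cov(P,B)/Var(B) = (ρw - ρb)/(1 - ρb)
- Adjustment: 3(1 - ρw) - 2(1 - ρw)²/(1 - ρb) + h

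Since ρw < 1, the best coefficient is below 1 for every ρb from 0 to ρw.

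**Numbers before adding h.** Subtraction gives 3 × 0.18 = 0.540 (walking time) and 3 × 0.13 = 0.390 (reach). Adjustment gives:
- ρb = 0.3, coefficients 0.74 and 0.81: 0.540 - 0.0648/0.7 = 0.447; 0.390 - 0.0338/0.7 = 0.342.
- ρb = 0.5, coefficients 0.64 and 0.74: 0.540 - 0.0648/0.5 = 0.410; 0.390 - 0.0338/0.5 = 0.322.

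**Variance ratio, subtraction to adjustment, with h added to each.**

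| ρb | h | Walking time | Reach |
|---|---|---|---|
| 0.3 | 0.2σ² | 0.740/0.647 = 1.14 | 0.590/0.542 = 1.09 |
| 0.3 | 0.5σ² | 1.040/0.947 = 1.10 | 0.890/0.842 = 1.06 |
| 0.5 | 0.2σ² | 0.740/0.610 = 1.21 | 0.590/0.522 = 1.13 |
| 0.5 | 0.5σ² | 1.040/0.910 = 1.14 | 0.890/0.822 = 1.08 |

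Taking square roots, the standard error with subtraction is about 5 to 10% larger for walking time and 3 to 6% larger for reach. At ρb = 0.5 and h = 0.2σ², subtraction would need about 60 × 1.21 = 73 women (walking time) or 60 × 1.13 = 68 (reach) to match adjustment with 60.

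**Why these assumed values.** The instruction to "refrain from using any drugs for or tobacco cigarettes beginning at midnight prior to each session" and a visit gap with no stated maximum leave room for day-to-day variation, so ρb may be well below ρw. Eligibility rests on "current cannabis use (within 6 months) based on self-report", so response is unlikely to be uniform and h is unlikely to be zero. Neither argument supplies a number.

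**Sensitivity.** With h = 0 the ratios are 1.32 and 1.21 at ρb = 0.5, and 1.67 and 1.41 at ρb = 0.7. In the other direction, if post-dose SDs were 20% larger than baseline and ρb = 0, the ratios would be 1.00 and 1.01, so the gain would vanish.

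**Cost of estimating the slope.** This is about 2% of variance. In simulation (30 vs 30) at ρb = 0.5, the HIV-by-drug ratios for h = 0.2σ² and 0.5σ² were about 1.16 to 1.20 and 1.12 to 1.13 (walking time), and 1.10 to 1.11 and 1.06 (reach). Type I error was 4.7 to 5.4% with subtraction and 4.5 to 5.3% with adjustment.

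**The case against.** The strongest reply is that nothing is wrong with the planned analysis. Difference-in-differences is standard and prespecified, it answers the question about declines from baseline, and it matches the power basis. That stands: the point is about efficiency only.

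Second, the size comes from outside the documents. ρb and h appear nowhere, and the power paragraph does not say whether its correlations are within-visit or between days. Reproducing 0.27σ² supports the variance formula, not that reading. This also stands, and is why the ratios are only an illustration. The direction is firmer: apart from the slope-estimation cost, the least-squares coefficient cannot give a larger variance than a fixed coefficient of 1, whatever the covariance structure.

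Third, adjustment relies more on the absence of one kind of carryover. Suppose 0.2σ carries over after active cannabis (walking time, ρb = 0.5 or 0.7). If it lasts through the whole visit 2 session, the drug effect is unbiased with subtraction and biased by -0.04σ or -0.06σ with adjustment. If it touches only the visit 2 baseline, the bias is +0.10σ with subtraction and +0.06σ or +0.04σ with adjustment. Neither method wins in both cases. The HIV interaction is biased only if carryover differs by HIV status.

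A reader might also object that HIV status is not randomized, so baseline adjustment could distort the group comparison. Here the covariate is a between-visit difference, whose expectation is zero in both HIV groups without carryover once order is in the model.

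**Conclusion.** The point holds as a modest gain in precision. The plan fixes the baseline coefficient at 1. With within-visit correlations of 0.82 and 0.87 and equal SDs, the best value is lower for any ρb from 0 to ρw. With assumed ρb of 0.3 to 0.5 and h of 0.2σ² to 0.5σ², the variance ratio is about 1.10 to 1.21 for walking time and 1.06 to 1.13 for reach, slightly less once the slope is estimated. It is larger if ρb is higher or h is near zero.

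Three stronger readings are tempting, and the documents support none of them:
- **That subtraction biases the result.** The baseline is pre-dose, the order is counterbalanced, and simulated type I error is nominal.
- **That the loss is large.** In the limit ρb = ρw with h = 0 the ratio reaches 3, and once ρb exceeds 2ρw - 1 (0.64 and 0.74) subtraction does worse than ignoring baseline. No stated figure places ρb there.
- **That the walking-time figure carries over to gait speed.** "Gait speed is measured under normal walking and attention-demanding conditions", but the correlation given is for walking time. Speed is proportional to the reciprocal of time, so its correlation depends on a distribution the plan does not describe. SART has no figure at all. Only reach, among the primary outcomes, has a directly matching correlation.

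**What to change.** Make the primary 15/60-minute analysis a regression of the active-minus-inactive post-dose mean on the active-minus-inactive baseline difference, HIV status and visit order. Code HIV status and order ±0.5 and leave the baseline difference uncentred. The intercept is then the average drug effect at equal baselines, and the HIV coefficient is the HIV-by-drug interaction. Centring the baseline difference at its mean would return the unadjusted drug effect.

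To retain women with only one session, the equivalent mixed model may be used: drug, HIV status, their interaction, visit, session baseline, the woman's mean baseline and a random subject effect. The mean baseline is needed so that the slope is the within-woman one. Keep the baseline-subtracted analysis as a sensitivity analysis.

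The costs are SAP wording, about two degrees of freedom (58 to 56), a stated assumption of negligible carryover into the visit 2 session and, for the difference regression, loss of women with only one session. No new data are needed.
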